Delirium in critical illness is estimated to cost \$4 to \$16 billion annually.³ Delirium increases ICU cost, hospital cost, complications, and mortality. A recent meta-analysis concluded that compared to patients without delirium, delirious patients were six times more likely to experience complications, had 7.22 days longer duration of mechanical ventilation, 7.32 days longer ICU length of stay, and 6.53 days longer hospital length of stay.⁴ Further, patients who experience delirium have problems with cognitive function and health status after hospital discharge, which have been documented at 3 and 12 months and may persist indefinitely.^{18,25,26} Because of the extensive incidence and significant negative outcomes associated with delirium, identification of effective interventions to reduce delirium is critically important. The Society of Critical Care Medicine, in its most recent guidelines for managing pain, agitation, and delirium in the adult critically ill,³ recommended routine assessment for delirium in the ICU and stated that the study of delirium in mechanically ventilated patients may lead to important advancements in the treatment of critically ill patients. A primary goal for the critically ill patient is to provide patient comfort while maintaining a level of arousal sufficient to follow commands. As a result of trends toward lighter sedation, most patients are aware of the ICU surroundings and require consistent and frequent reorientation to all aspects of their care.

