The cognitive reorientation intervention we have developed and pilot tested is a simple but potentially powerful strategy to provide structured information in a familiar voice to patients on a regular basis. Because the intervention has a strong nursing care focus, it has the potential to affect delirium in ways that are distinct from but synergistic with medical care, which has focused primarily on pharmacologic management of delirium. The FAVoR intervention we propose in this project holds promise for reducing delirium in critically ill adults, improving sleep in the ICU, and secondarily benefitting cognitive function post-ICU.

We will accomplish the objectives using a prospective, randomized, experimental design to achieve robust and unbiased results. Subjects (n=182) will be randomly assigned within 48 hours of ICU admission and intubation to one of two groups. In the intervention group, scripted audio messages recorded by the patient's family (FAVoR) will be played for the patient at hourly intervals during daytime hours. These messages will be personalized, delivered automatically, and provide information about the ICU environment. Subjects in the control group will not receive recorded audio FAVoR messages. The FAVoR intervention, a standardized protocol developed and tested in preliminary work, will be delivered by audio recording for 5 consecutive days (120 hours), or until ICU discharge if discharge occurs within the first 5 days. The number of episodes of delirium during ICU stay is the primary outcome measure. We will also collect data at 1 month and 6 months following ICU stay for secondary aim 3. A model of the study is presented in Figure 1.

IRB Study Number: 20170771, Version #1.8, Date: 03/10/21, PI: [name]

[figure not shown]
Preliminary Studies

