- 1) **Intervention Group:** Subjects in the intervention group will receive personalized digitally recorded reorientation messages administered for up to 2 minutes every hour over an 8-hour daytime period (beginning at 9 am daily) recorded in the voice of a family member. Subjects in the intervention group will continue to receive the intervention for up to a total of 5 days (120 hours), or until ICU discharge if ICU discharge occurs within the first 5 days. Since in the ICU setting delirium has a mean onset of 2.6 days (S.D. +/- 1.7), and a mean duration of 3.4 +/- 1.9 days,⁴⁹ a 5-day period for the study intervention is appropriate and includes the period prior to delirium onset as well as when delirium has been shown to occur most frequently.
- 2) **Control Group:** The control group will consist of usual care, and will not receive audio reorientation messages. Subjects will remain in the study for five days or until ICU discharge if discharged before five days.

Subjects in both groups will be reoriented by care providers as part of usual care practices. Data will be collected from the medical record daily. Both groups (intervention and control) will undergo longitudinal cognitive and patient-reported health status evaluations concurrently with 24-hour sleep profiler-polysomnography and actigraphy at three different points in time. The first time point is inpatient, at least 24 hours after ICU discharge, then outpatient with two home visit data collection events at 1 month and 6 months post hospital discharge.

Description of Intervention. The FAVoR intervention includes a set of 8 recorded messages which were developed in preliminary study 1, and were tested and refined in preliminary study 2. Based on the feasibility data (preliminary study 2) each message is scripted, is no longer than

IRB Study Number: 20170771, Version #1.8, Date: 03/10/21, PI: [name]

2 minutes long, is a personal message using the subject's name, uses simple terms, and is written at a 5th grade reading level. Messages include information about the critical care environment, the visual and auditory stimuli to be expected, and the availability of providers and family. The messages call the patient by name (preferred name as recommended by the patient's family); we believe the use of the patient's name may create greater attention to the message.

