3. SP-PSG (substituted by PROMIS-SD and PROMIS-SRI)
4. NIH Toolbox Cognition Battery (substituted by PROMIS-CF and PROMIS-CFA)

Delirium. The primary outcome measure for this project is delirium free days. We will quantify delirium using the Confusion Assessment Method for the ICU (CAM-ICU).⁴⁵ CAM-ICU scores for each subject will be obtained by study personnel twice daily at 9 am and 4 pm (coinciding with the schedule for initiation and conclusion of messages each day in the FAVoR intervention group, and at identical times for the control group). CAM-ICU scores will also be recorded at the same times for two days following the completion of the intervention period. The Confusion Assessment Method (CAM) will be used during study visits after transfer from the ICU (post ICU, 1 month, and 6 month follow up periods) for comparison.

We will also collect documentation by providers in the medical record of episodes of delirium occurring outside of the CAM-ICU data collection conducted by research personnel. Only days without any instances of delirium will be counted as delirium free days. The CAM-ICU is recognized in the Clinical Practice Guidelines for the Management of Pain, Agitation, and Delirium in Adult Patients in the Intensive Care Unit as a valid, reliable, and feasible tool to detect delirium in ICU patients³ with pooled sensitivity of 75.5% and specificity of 95.8%.⁵⁰

Sleep/Activity. Sleep patterns in the critically ill are highly disorganized, with fragmentation, a predominance of light sleep, and reduction in deep sleep and rapid eye movements.⁸ We will use the FDA approved Sleep Profiler system (Advanced Brain Monitoring, Carlsbad, CA) to obtain continuous polysomnography data (SPPSG). The Sleep Profiler has been successfully utilized in mechanically ventilated and sedated patients and provides three frontopolar electroencephalographic (EEG) signals (AF7/AF8, AF7/Fpz and AF8/Fpz).⁵¹⁻⁵⁴

A wrist actigraph (ActiWatch Spectrum, Philips Respironics, Bend, OR) will be placed on the wrist to measure patient activity and ambient light levels. We have extensive experience with

IRB Study Number: 20170771, Version #1.8, Date: 03/10/21, PI: [name]

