There will be two parts of the data analysis: Part I: A traditional statistical data analysis for randomized controlled trials for the Primary Specific Aim, and Part II: Pathway analytic model analyses to address the secondary aims. [name] will work closely with the Data Manager to perform all the planned data analyses for this study.

Part I: We will follow the research and regulatory guidelines for statistical analysis of clinical trials including the ICH Guideline⁷⁷ and the CONSORT guidelines⁷⁸. First, descriptive statistics will be performed to describe and compare the characteristics of the intervention and the control groups. Descriptive statistics will be reported as means +/- standard deviation for continuous variables and as frequencies and percentages for categorical variables. Shapes of the data distributions, missing data and outliers will be examined by both graphics and statistical tests. Any data issues identified will be discussed with the PI and other investigators and addressed before formal data analysis. For example, skewed variables may be transformed so that their distributions are close to the Normal Distribution. Outliers may be excluded or included in two separate analyses. Missing data may be imputed or handled by other missing data techniques. Distributions of continuous variables and categorical variables will be compared between the intervention and the control group by using the t-test or Wilcoxon rank sum test and the Chisquare test, respectively. Any baseline covariate that is differentially distributed in the two groups will be adjusted in the subsequent analysis for testing the intervention effect. Assuming the randomization produces well balanced intervention and control groups, a Chi-square test for a 2x2 table with the number of delirium free days and the treatment assignment will be performed to test the primary hypothesis. If there are unbalanced covariates, then covariance adjustment will be performed by using logistic regression that includes both the treatment assignment and the unbalanced covariates. If there are missing values in the primary outcome, then multiple imputation will be performed using SAS PROC MI for missing at random (MAR) data.^{79,80} Sensitivity analysis for potentially not missing at random data will be performed using the Yau and Little⁸¹ Intent-to-Treat Analysis for Longitudinal Studies with Dropouts.

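### The primary score counts delirium free days with no denominator, fixed window or discharge rule, so length of ICU stay can dilute a FAVoR effect

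*Combined protocol and SAP*

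**What the plan says.** Section 9 (Key Variables and Their Measurement, Delirium) states: "The primary outcome measure for this project is delirium free days". The counting rule follows: "Only days without any instances of delirium will be counted as delirium free days". CAM-ICU is scored twice daily, and "CAM-ICU scores will also be recorded at the same times for two days following the completion of the intervention period"; Table 1 labels these as ICU Days 6-7. For the control group, section 9 adds: "Subjects will remain in the study for five days or until ICU discharge if discharged before five days". The intervention likewise runs for 5 days or until earlier ICU discharge. After that the assessment changes: "The Confusion Assessment Method (CAM) will be used during study visits after transfer from the ICU", which means visits and not daily scoring.

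Section 10 (Data Analysis Plan, Part I) gives the primary test: "a Chi-square test for a 2x2 table with the number of delirium free days and the treatment assignment will be performed". It states no cut that would turn a count into two levels. Multiple imputation is planned for missing primary outcome values, but the plan does not say whether days after ICU discharge are missing, free or not counted.

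Section 4 names a different primary outcome: "The number of episodes of delirium during ICU stay is the primary outcome measure". Its Significance part also cites, for patients with delirium, "7.32 days longer ICU length of stay".

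**The concern.** The hypothesis in sections 3 and 10 is that FAVoR subjects have less delirium. A raw count of free days measures two things at once: how little delirium a subject had, and how many ICU days were available to be counted. Nothing in the plan separates them. This arises with complete data and identical windows in both arms.

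If delirium lengthens the ICU stay, a subject spared delirium leaves sooner and loses countable days, while a delirious subject stays and gains some. Part of the benefit then subtracts from the primary score. Early death or withdrawal shortens the count in the same way. At stake is whether the primary comparison can show an effect that is really there.

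**Working it through.** **The plan's own figure.** The documents give no planned value for the free-day count. The only related figure is the sample size in section 8: 95% power, W = 0.35, alpha 0.05, 40% attrition, 182 in total. With noncentrality N × W², a 2 df test needs 127 and a 1 df test needs 107. Then 127 × 1.4 = 178, 107/0.6 = 179 and 127/0.6 = 212. The stated 182 is within 3% of the first two. I take from it only 91 per arm and W = 0.35.

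**Inputs from the documents.** Delirium in up to 80% (section 4); onset 2.6 (SD 1.7) days and duration 3.4 (SD 1.9) days (section 9); 7.32 more ICU days with delirium (section 4); expected ICU stay of at least 48 hours (section 20); window of 5 or 7 days.

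**Scoring by hand.** Score = observed ICU days − delirium days.
- A, never delirious, leaves after day 3: 3 − 0 = 3.
- B, in the ICU 7 days, delirious on 3: 7 − 3 = 4.
- C, in the ICU 7 days, never delirious: 7 − 0 = 7.

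Over 7 days B outranks A. Over 5 days, with B's three delirium days inside them, B scores 5 − 3 = 2 and A still scores 3, so this pair is ordered correctly.

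**At the protocol's mean onset and duration.** Delirium runs from 2.6 to 2.6 + 3.4 = 6.0 days. A delirious subject who stays scores 5 − 2.4 = 2.6 over 5 days, or 7 − 3.4 = 3.6 over 7. A never-delirious subject leaving after day 2 scores lower in both windows; after day 3, lower only over 7 days; after day 4 or later, in neither.

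**Simulation.** W = (|p1 − p2|/2)/√(m(1 − m)), with m the mean of p1 and p2. For p1 = 0.80 and W = 0.35, p2 = 0.46: 0.169/√(0.631 × 0.369) = 0.35. Assumptions not in the documents: this FAVoR rate; mean stay of never-delirious subjects (varied below), with the delirious stay parameter 7.32 days longer; minimum stay 2 days; exponential stays; onset counted from the first study day; no deaths. There were 1,000 trials of 91 per arm per row. The fixed-window score counts days after discharge as free.

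| Window | Mean stay, never delirious | Mean gain, raw count | Mean gain, fixed window | Share kept | Pairs with never-delirious lower | Rank-test power, raw count |
|---|---|---|---|---|---|---|
| 7 days | 3 | 0.19 | 1.09 | 17% | 27% | 14% |
| 7 days | 4 | 0.44 | 1.11 | 40% | 19% | 44% |
| 7 days | 5 | 0.63 | 1.12 | 56% | 15% | 63% |
| 7 days | 7 | 0.81 | 1.13 | 72% | 10% | 80% |
| 7 days | 20 | 1.11 | 1.19 | 93% | 3% | 96% |
| 5 days | 3 | 0.37 | 0.82 | 45% | 8% | 50% |
| 5 days | 4 | 0.51 | 0.81 | 63% | 5% | 70% |
| 5 days | 5 | 0.61 | 0.82 | 74% | 4% | 82% |
| 5 days | 7 | 0.69 | 0.82 | 84% | 2% | 90% |
| 5 days | 20 | 0.81 | 0.85 | 95% | 1% | 95% |

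Rank-test power for the fixed-window score or the fraction of ICU days was 96-99% throughout.

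**Other assumptions.** With 80% vs 50% delirium and differently shaped stays, 7-day raw-count power was 18%, 57% and 76% at base stays of 4, 6 and 8 days, against 95% for the fraction. Another run gave 10%, 26%, 56% and 70% at 3, 4, 6 and 8 days, against 93-96%. With only 2 extra ICU days for delirium, that run gave 32-74% against 90-95%.

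**If delirium does not cause the longer stay.** When the 7.32 days were tied to a patient's susceptibility instead (80% vs 50%, base stay 4 to 8 days), free-day differences were 1.02-1.08 against 1.04-1.09 delirium days averted over 7 days. Raw-count rank power was 86-95% across two such runs and both windows.

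**The 2x2 table.** With 80% vs 46%, a chi-square on any vs no delirium had about 99-100% power in every row. A median cut on the raw count had 39-77%.

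**The case against.** The strongest reply is that the plan uses a chi-square test on a 2x2 table, not a rank test. If the cut is any vs no delirium, an early leaver without delirium is simply a success and nothing is lost. That is right as far as it goes, but the plan does not state that cut, and the text names the number of free days. Section 4's episode count would also rank A (0) ahead of B (at least 1), but that is a conflict to resolve, not a rule to rely on.

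The 7.32 days is a comparison of patients with and without delirium. Sicker patients may both stay longer and become delirious, in which case dilution nearly vanishes. This stands, and it makes the size of the loss conditional.

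A reader might infer that participation ends at ICU discharge and later days score zero. The documents do not say so: subjects continue to a post-ICU evaluation and to 1 and 6 months, and Table 1 collects CAM and provider-documented delirium 24-72 hours after ICU discharge. The plan is silent on scoring those days, and daily CAM-ICU is not planned for them.

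The fraction is not perfect either. Two subjects with 3 delirium days score 1/4 = 0.25 free if observed 4 days and 4/7 = 0.57 if observed 7. A non-delirious subject who dies on day 2 scores 1.0. This stands too: a fixed window is an equally sound choice, and deaths need their own rule under either.

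**Conclusion.** The concern holds as a defect in how the primary score is defined. The count has no denominator, window, discharge rule or death rule, so its ceiling is the subject's own observed ICU days. Some never-delirious early leavers rank below delirious stayers, and if delirium prolongs the stay, a real effect is diluted and could be masked.

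Across all the simulations, raw-count rank-test power ran from about 10% to 96%, against about 90-99% for an anchored score. The loss is severe where never-delirious subjects leave at about 3 to 5 days and the window is 7 days. It is small where nearly everyone stays through the window or where delirium does not cause the longer stay. ICU stay, the FAVoR delirium rate, the distribution shapes and the absence of deaths are assumptions.

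Three stronger readings are not supported. Not every early leaver is misranked. A real effect is not certainly hidden. The low percentages are not powers of the planned chi-square test, which cannot be computed until its cut is stated.

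**What to change.** Amend section 9 (Delirium) and section 10 (Part I) before outcomes are compared by arm:

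1. Replace the raw count with a score that does not rise with length of stay. Either use delirium days out of observed ICU days, in a model weighted by days observed, or delirium free days over one fixed window with a stated scoring rule for days after ICU discharge.
2. Name the window, 5 or 7 days.
3. Score deaths by a stated rule so that early death is not counted as benefit, and report observed ICU days by arm.
4. Derive the 2x2 table from a stated cut that length of stay does not drive, such as any vs no delirium, under the same window and death rule. Do not cut the raw count.
5. Reconcile section 4, which names the number of delirium episodes, with section 9.

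The cost is wording and one derived variable, observed ICU days, from data already collected. No patients, visits or staff are added. The downside is small: fractions from short stays are imprecise, and a fixed window must assume a status for unassessed days after discharge.

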Duration of Intervention and Data Collection Procedures. Following consent, the duration of participation includes data collection over a maximum of 120 hours (5 days) of the ICU stay, overnight data collection at least 24 hours following ICU discharge, and overnight data collection during home visits at 1 and 6 months following hospital discharge. Multiple subjects (up to a maximum of 4) will be actively enrolled in this study as inpatients and outpatients, using research equipment obtained for this study (multiple wireless speakers, Sleep Profilers, and actigraphy watches) to achieve the collection of key variables in Table 1.

As of March 2020, per the updated guidance regarding research continuity from the University of Miami IRB and research administrations, we are complying with the COVID-19 safety recommendations to protect our subjects, research personnel, students, and faculty members.

As of June 2020, we will resume new enrollments at UMH; temporary pause of enrollments at JMH continues. We will deliver interventions and collect face-to face data at UMH. We will not collect data that can only be collected face-to-face during follow up visits. We will schedule and conduct follow-up visits by phone or video conference calls, and we will substitute NIH PROMIS measures (including PROMIS Global Health, PROMIS-SD, PROMIS-SRI, PROMIS-CF,

IRB Study Number: 20170771, Version #1.8, Date: 03/10/21, PI: [name]

PROMIS-CFA) for the Sleep Profiler and Actigraphy measures, until it is safe to resume face-to-face interactions with subjects at follow-up.

Please refer to the updated Table 1 for a detailed list of which data will be collected remotely via the electronic medical record and from the subject over the phone or via video conference.

Table 1. Key Variables and Data Collection

Concept	Measure	Data Collection Time Points						
		24 hours Pre-Study	Study Admission	ICU Days 1-5	ICU Days 6-7	24-72 hours Post-ICU Discharge	1 Month Post-Hospital Discharge	6 Months Post-Hospital Discharge
Delirium ICU delirium Post-ICU delirium Provider report of delirium	CAM-ICU		*	*	*			
	CAM					*	***	***
	Documentation of delirium	**	**	**	**	**		
Activity/Sleep	Actigraphy SP-PSG		*	*		*	*	*
			*	*		*	*	*
Iatrogenic, Environmental, and Biobehavioral Factors Ambient light Pharmacological therapies affecting sleep and/or cognition Disease severity and comorbid conditions Demographic characteristics	Actigraphy		*	*		*	*	*

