Inpatient. Once consent is obtained and the subject is enrolled, baseline data will be collected from medical records. In randomized assignment to the intervention group, the family member selected by the family to record scripted FAVoR messages will be contacted, and taken to a quiet area to complete the recording on the assigned computer. FAVoR will be delivered through a wireless speaker, which will be placed near the patient's head. Delivery of the intervention to subjects randomized to receive it will begin as soon as possible during 9 am and 4 pm; if the FAVoR messages cannot be recorded before 4 pm, the intervention will begin on the following morning at 9 am. Data recording devices (SP-PSG and ActiWatch) will be applied to the subjects receiving the intervention immediately prior to the onset of the FAVoR intervention, and to control subjects as soon as feasible following consent. Actigraphy and SPPSG will continue throughout the 120-hour period beginning with the intervention delivery and continuing until the same time 5 days (120 hours) later. Data collection will resume and continue after at least 24 hours of ICU discharge. The subject will complete the NIH Toolbox-Cognition Battery, and the PROMIS Global Health instrument, and actigraphy and SP-PSG will be obtained.

We will follow University of Miami Hospital and Jackson Memorial Hospital infection control policies and procedures for cleaning portable equipment before and between patients, which include appropriate germicidal or bleach agents and single use disposable equipment covers.

As of June 2020, we will resume data collection at UMH for the following measures: CAM-ICU, Actigraphy, SP-PSG, and the NIH Toolbox Cognition Battery. Data collection remains paused for these measures at JMH.

Outpatient. There will be two outpatient data collection events at 1 month and 6 months posthospital discharge. During the 1 month home visit, research staff will travel to the subject's home (or other location agreed upon) to administer the NIH Toolbox-Cognition Battery testing and the PROMIS Global Health assessment, PROMIS-SD, PROMIS-SRI, PROMIS-CF, PROMIS-CFA questionnaires. While face-to-face interaction is not permitted, the subjects will not be asked to wear the SP-PSG and ActiWatch (for acquisition of sleep and activity data) overnight. Identical data collection processes will be used at the 6 month visit.

Procedures for telephone or video conference:

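### In-ICU sleep recording starts at a different event in each arm, which leaves the sleep comparison in exploratory secondary aim 1 open to bias

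*Combined protocol and SAP*

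**What the plan says.** Section 9, Inpatient, gives the two arms different starting events for sleep recording. The SP-PSG and ActiWatch are applied to FAVoR subjects "immediately prior to the onset of the FAVoR intervention, and to control subjects as soon as feasible following consent".

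Only the FAVoR start depends on a further step after assignment: "the family member selected by the family to record scripted FAVoR messages will be contacted", and the recording must then be made. There is also a cut-off: "if the FAVoR messages cannot be recorded before 4 pm, the intervention will begin on the following morning at 9 am".

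The length of recording is tied to the same arm-specific event: "Actigraphy and SPPSG will continue throughout the 120-hour period beginning with the intervention delivery". No equivalent starting point is given for controls. The control-group description in Section 9 says five days or until ICU discharge, without saying from when. Section 7 describes participation after consent as "data collection over a maximum of 120 hours (5 days) of the ICU stay".

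Table 1 in Section 7 lists actigraphy and SP-PSG at Study Admission and again for ICU Days 1-5, without separating the arms.

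Sleep is the proposed mediator in secondary aim 1. Part II of the Data Analysis Plan (Section 10) specifies mediation analysis within a multilevel structural equation model. Neither part of that plan aligns the recording windows, defines a common first night or adjusts for start time.

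**The concern.** The start rule operates after randomisation and depends on arm, so randomisation does not balance it. Two subjects consented at the same hour can be recorded over different stretches of their ICU stay only because of their assignment.

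This matters in two ways. First, if sleep changes with time since intubation, part of any difference between arms reflects when recording took place. Section 20 describes patients in the first 48 hours of intubation as always sedated to some degree, so a change over these days is plausible. Second, a delayed FAVoR subject who leaves the ICU before the first message has no in-ICU sleep recording, while a control with the same course may have one. Early exit then removes subjects differently in the two arms. Both problems fall on the arm-to-sleep path, the first link of the mediation analysis.

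**Working it through.** The plan states no figure on this point, so there is none to reproduce. The check is clock arithmetic.

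**Inputs from the documents**
- FAVoR start if the cut-off is missed: 9 am next day (Section 9, Inpatient).
- Window length: 120 hours (Sections 7 and 9).
- In-person staffing: about 8 am to 6 pm (Section 20), so a control can be fitted after 4 pm on the day of consent.

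**Assumptions not in the documents**
- The control is fitted at the hour of consent, the earliest reading of the rule.
- Night is 22:00 to 06:00.
- A same-day family recording takes 1 hour.

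**Step 1: lag between arms.** Lag = FAVoR start minus control start; overlap = 120 minus lag.

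| Consent | FAVoR start | Lag | Overlap of the two windows |
|---|---|---|---|
| 9 am, cut-off missed | 9 am next day | 24 h | 96 h |
| 4 pm | 9 am next day | 17 h | 103 h |
| 6 pm | 9 am next day | 15 h | 105 h |
| 9 am, recorded same day | 10 am same day | 1 h | 119 h |

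For the 4 pm consent, 17/120 = 14% of the window.

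**Step 2: nights covered.** In each missed-cut-off case the lag contains one whole assumed night (8 of 8 hours). Both full windows hold 5 nights (5 × 8 = 40 night hours), but the control covers nights 1-5 after consent and the delayed FAVoR subject nights 2-6. With same-day recording no night is lost.

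**Step 3: early ICU discharge.** Take consent at 4 pm and a FAVoR start 17 hours later.

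| ICU discharge after consent | Control nights | Delayed FAVoR nights |
|---|---|---|
| 24 h | 1 | 0 |
| 48 h | 2 | 1 |
| 72 h | 3 | 2 |
| 96 h | 4 | 3 |
| 120 h | 5 | 4 |
| 144 h | 5 | 5 |

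**Step 4: scale, for illustration only.** The one indication of drift in sleep is the feasibility trial (Section 4, preliminary study 2). Control sleep efficiency went from 54% to 52%, a change of -2 points. Spread over an assumed 1 to 3 nights, that is -2/1 = -2 to -2/3 = -0.7 points per one-night shift. The pilot contrast in change was (66 - 56) - (52 - 54) = 12 points. With 10 subjects per arm and actigraphy obtained in 23 of 30, this drift is too imprecise to fix a sign or size. It also says nothing about early exit, and the drift effect on the arm mean would be scaled by the unknown share of FAVoR subjects delayed.

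**The case against.** The strongest reply is that the lag may be rare and short. An available and willing family member is required before enrolment, and the visiting difficulty described in Section 20 concerns finding family before enrolment, not the wait after assignment. Section 20 also allows recording by phone or Zoom. Controls are fitted only when feasible, so one consented late in the day may also wait until morning. The affected aim is worded as exploratory, and because recordings can be placed by clock time, analysis could repair much of the problem. All of this stands. It limits the likely size, but the arm-dependent rule remains, and the plan contains no such analysis.

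Three stronger readings are tempting, and the documents do not support them.
- **The sleep comparison is biased.** The share delayed, the direction and the size are all unknown.
- **The primary delirium outcome is shifted too.** The device sentence covers only SP-PSG and the ActiWatch. Section 9 (Delirium) sets CAM-ICU at 9 am and 4 pm in both arms, and Table 1 lists it at Study Admission. Nothing ties the CAM-ICU schedule to device application, and the delirium onset times quoted in the protocol do not measure a sleep effect.
- **FAVoR subjects have no recording before the first message.** Section 9 implies this, but Table 1 places both devices at Study Admission for all subjects. The two places conflict and need reconciling; the absence cannot be stated as fact.

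**Conclusion.** The point holds for the in-ICU sleep recordings. The plan gives the arms different starting events, leaves the control window without an anchor and has no rule to align the two. A FAVoR subject whose recording misses the cut-off starts about 15 to 24 hours after a control consented at the same time, covers nights 2-6 instead of 1-5, and has one recorded night fewer at each of the discharge times checked from 24 to 120 hours after consent. This rests on the control being fitted at consent and on the assumed night hours. With same-day recording the lag is about 1 hour.

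The sleep comparison used for mediation in secondary aim 1 is therefore open to bias from time since intubation and from differential early exit. The recordings after ICU discharge and at 1 and 6 months are not shown to be affected, nor is the primary outcome.

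**What to change.** **Section 9, Inpatient.** Apply SP-PSG and actigraphy in both arms at the same event, as soon as feasible after consent and randomisation, and run the 120-hour window from that event in both arms. Reconcile the text with the Study Admission column of Table 1.

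**Section 10, Data Analysis Plan.** Number ICU nights from randomisation in both arms and analyse sleep on that common clock. A new device rule cannot reach subjects already recorded under Version 1.8 or before. For them, use the recording times to restrict the analysis to shared nights since randomisation, or to adjust for night since randomisation.

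**Cost.** The text changes are short, but there is a trade-off. Section 7 caps ICU data collection at 120 hours, and Sections 8 and 13 have the devices removed once collection is complete, within the same limit. If that limit stays, a window opened at the common event may miss the last hours of a delayed message period (17 hours in the 4 pm example). Recording those hours as well would mean changing those sections too. A common start event removes the planned lag between arms; differences in when fitting proves feasible would remain and should be reported by arm.
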